8.7 Microbial Profiles in Pooled Supragingival Plaque

The pooled supragingival plaque samples collected from the mesiobuccal surfaces of the Ramfjord teeth at the baseline, Day 14 and Day 28 visits will be analyzed for the presence of pathogenic organisms. The frequency and percent of the presence of the following organisms will be summarized (tables, listings and checkerboard plots) by study arm and visit:

Fusobacterium nucleatum subspecies vincentii, *Campylobacter concisus*, *Campylobacter rectus*, *Tannerella forsythensis*, *Prevotella intermedia*, *Prevotella nigrescens*, *Porphyromonas gingivalis*, *Capnocytophaga sputigena*, *Streptococcus oralis*, *Actinomyces naeslundii*, *Actinomyces israeli*, *Eubacterium brachy*, *Eikenella corrodens*, and spirochetes. The table and figure will also capture the frequency and percent of subjects with microbial counts missing.

8.8 Vital Signs, Physical Findings, and Other Observations Related to Safety

8.8.1 Vital Signs

The vital sign parameters will include sitting pulse rate, respiration rate, blood pressure (systolic (SBP) and diastolic (DBP)), and body temperature (oral). All vital signs and weight values will be listed, by subject. Out-of-range flags (H or L) will be used to denote abnormal values. The abnormal values will be identified based upon the clinically significant criteria CS as listed in Table 9.8.1.1. In addition, all treatment-emergent CS vital sign values or weights will be listed separately, by subject, with relevant subject information.

The actual vital sign values and the change from baseline values will be summarized at all assessment times. Summary statistics will include n, mean, SD, median, minimum, maximum values, and the number and percent of subjects with missing values for the vital sign measure.

Table 8.8.1.1 CS Criteria for Vital Signs

Parameter	PCS Criteria
Vital Signs	
Blood pressure (sitting)	
Diastolic	< 50 mmHg, %, with decrease from BL \geq 15 mmHg; or > 105 mmHg, with increase from BL \geq 15 mmHg
Systolic	< 90 mmHg, %, with decrease from BL \geq 20 mmHg; or > 180 mmHg, with increase from BL \geq 20 mmHg
Heart rate (sitting)	< 50 BPM, with decrease from BL \geq 10 BPM; or > 120 BPM; or Change from BL \geq 30 BPM
Temperature (oral)	> 101°F or 38.4°C, with increase from BL \geq 2°F or 0.75°C
Weight	Change from BL \geq 7% body weight

BL=Baseline

8.8.2 Oral Exam

All oral exam findings will be listed by subject. Any treatment-emergent abnormal findings will be listed. Subjects will be considered to have a treatment-emergent abnormal finding if the subject has a normal assessment for a specific oral structure at the baseline visit and is assessed as having an abnormal finding at a post-baseline study visit. A table will summarize by the number and percent of subjects that have treatment-emergent abnormal findings for each oral structure. This table will also summarize for each oral structure the number and percent of subjects that improve or have no change in normal/abnormal status from the Baseline visit. The number and percent of subjects with missing values due to early withdrawal or otherwise will be summarized in the table for each oral structure.

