5 STUDY ENROLLMENT AND WITHDRAWAL

Approximately 125 healthy adult male and female subjects with gingival inflammation, determined by mean full mouth MGI of at least 2.0, will participate in the study. The inclusion and exclusion criteria are as follows:

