5.1 Subject Inclusion Criteria

1. Signed consent form;
2. Good general health as evidenced by medical history;
3. Age 18 through 65 years;
4. Stable address;
5. Availability for the duration of the study (if a subject does not meet this criterion, he/she may be rescreened for study participation when he/she does meet this inclusion criterion);
6. Minimum of 20 natural teeth, excluding third molars;
7. Mean full mouth MGI of at least 2.0;
8. Willing to use prescribed oral hygiene procedures and products;

9. Stability of medications for chronic conditions for at least 3 months prior to enrollment (if a subject does not meet this criterion, he/she may be rescreened for study participation when he/she does meet this inclusion criterion);
10. For women of reproductive potential, use of licensed hormonal contraception or double-barrier methods;
11. For men of reproductive potential, agreement to use condoms;
12. Liver function test (aspartate aminotransferase [AST], alanine aminotransferase [ALT], alkaline phosphatase, and total bilirubin) levels equal to or less than 1.5 times the upper limit of normal;
13. Serum creatinine levels equal to or less than the upper limit of normal;
14. Subjects with complete blood count levels within 10% of the normal laboratory range and erythrocyte sedimentation rate equal to or less than 2 times the upper limit of normal.

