7.3 Enrollment/Baseline

Study Visit 1 - Enrollment/Baseline Visit (Day 0)

- Obtain and document consent from subject on study consent form.
- Review and confirm medical and dental history, including alcohol and tobacco use history, for study inclusion.
- Record vital signs (temperature, pulse rate, respiratory rate, blood pressure).
- Record current concomitant medications and dental procedures and update medication history for study inclusion.
- Obtain urine pregnancy test on women of childbearing potential. Study staff will record the test kit lot, expiration date, and result. Test must be documented as negative before continuing to conduct baseline procedures that follow.
- Perform intraoral and extraoral examinations, to include hard and soft tissue assessments (face, lymph nodes, lips, buccal mucosa, floor of the mouth, tongue, hard and soft palate, gingiva, edentulous ridges, and teeth).
- Collect GCF for baseline measurements of IL-1 β .
- Assess and record baseline MGI.
- Assess and record baseline PI.
- Obtain supragingival plaque samples for baseline analyses of oral bacteria.
- Assess and record baseline PD and GM-CEJ distance (to calculate CAL).
- Assess and record baseline BOP.
- Reconfirm eligibility prior to subject randomization based on information collected during Screening Visit and study Visit 1.
- Obtain approximately 15 mL blood for baseline BLXA4 level and specialized pro-resolution mediator (SPM) (lipoxins and resolvins) profiling.
- Randomize subject to 1 of the study arms, using a block randomization schedule.
- Provide study drug with instructions for use and a timer to be used while rinsing. A study team member other than the examiner will supervise the subject's first use of the medication.
- Provide subject with the memory aid and instructions for its use.
- Provide subject with a study contact number to call for AEs or questions.

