8.4 Adverse Events

All AEs will be coded to a system organ class (SOC) and preferred term (PT) using the most current version of the Medical Dictionary for Regulatory Activities (MedDRA). All tabular AE summaries will be for TEAEs. TEAEs will be defined as those AEs with an onset on or after the date of first dose of study drug (study visit 1: Day 0). If an AE was recorded prior to the first dose of study drug and there was an increase in its severity, the AE will be considered a TEAE. All other AEs will be classified as non-treatment-emergent. Treatment-emergent AEs will be flagged in all AE data listings.

An overall summary table will be developed to report the number of events and the incidence of participants having at least one event in the following categories:

- TEAEs
- TEAEs indicated as serious (SAEs)
- TEAEs that lead to study drug discontinuation
- TEAEs with an outcome of death
- TEAEs that were reported as having a definite/certain or possible relation to study drug
- TEAEs reported as having a severity rating of severe

In addition, a summary table of TEAEs classified by system organ class (SOC) and preferred term (PT) will be provided for each of the following:

- TEAEs
- TEAEs by maximum severity
- TEAEs by relationship to study drug

The summary of all TEAEs will present both the number of TEAEs and the incidence of TEAEs. The summary of TEAEs by severity, relationship to study drug, and week of treatment will only report the incidence of TEAEs. When reporting the number of TEAEs, if the same TEAE occurs for a subject on multiple occasions the event will be counted once for each occurrence. When reporting the incidence, a subject will only be counted once if they ever experience an event within the SOC and ever experience the individual PT.

For the summary of TEAEs by severity, if the severity of the TEAE is not reported, then the severity of the TEAE will be counted as severe. If the same TEAE occurs for a subject on multiple occasions, the TEAE will be categorized according to the highest severity rating for that TEAE in that subject. For the summary of TEAEs by relationship to study drug, if the relationship is missing, it will be counted as definite/certain. If the same TEAE occurs for a subject on multiple occasions, the TEAE will be categorized according to the closest relationship to study drug reported for that TEAE in that subject.

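### The SAP 8.8.2 oral exam table has no category for worsening of a structure already abnormal at baseline, so such worsening, above all of the gingiva, is tabulated as unchanged

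*SAP*

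**What the plan says.** SAP 8.8.2 lets a subject count as treatment-emergent only "if the subject has a normal assessment for a specific oral structure at the baseline visit"; that structure must then be recorded as abnormal later on. The same table also reports, for each structure, "the number and percent of subjects that improve or have no change in normal/abnormal status from the Baseline visit", together with missing values. The section adds that "All oral exam findings will be listed by subject".

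The gingiva is one of the structures examined. Protocol 7.3 ends its list of tissues with "hard and soft palate, gingiva, edentulous ridges, and teeth". Protocol 5 describes the subjects as having "gingival inflammation, determined by mean full mouth MGI of at least 2.0", and SAP 2.3 applies that threshold at both screening and baseline.

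SAP 6 says the baseline oral exam records each area as normal or abnormal, with a description if abnormal. Neither document says how the study gingivitis itself is to be coded on that form.

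Neighbouring rules do allow for worsening. The tables for OMAS scores (SAP 8.8.3) and tooth status (SAP 8.8.4) both have a worsened category. For an adverse event recorded before the first dose, SAP 8.4 says that if "there was an increase in its severity, the AE will be considered a TEAE". Protocol 12.5.1 likewise includes pre-existing conditions that get worse.

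**The concern.** The primary objective (Protocol 3.1, SAP 2.1) names mucosal inflammation and irritancy, and lists oral examination findings as a source of safety evidence. SAP 8.8.2 is the by-arm summary of those findings. A rule that can only register a change from normal to abnormal has no means of showing deterioration in tissue that starts out abnormal.

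The gingiva is where this matters most. It is in contact with the rinse, and every subject enters with it inflamed. The irritation signs seen in the rat study, erythema and edema (Protocol 2.5.1), are also features of the higher MGI grades (Protocol 8.1.2), so an irritant effect would look like more of the baseline disease. The OMAS table could register worsening, but its sites (Protocol 8.1.1) are the lips, palate and fauces, buccal mucosa, tongue and floor of the mouth, not the gingiva.

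A gingiva row with no treatment-emergent findings and nearly everyone unchanged could then be taken as reassurance about irritation when it reflects only the definition.

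**Working it through.** **Step 1. Apply the 8.8.2 rule to every combination of baseline and later status.**

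| Baseline | Later visit | Where 8.8.2 puts it |
|---|---|---|
| Normal | Normal | Unchanged |
| Normal | Abnormal | Treatment-emergent |
| Abnormal | Normal | Improved |
| Abnormal | Abnormal, same | Unchanged |
| Abnormal | Abnormal, worse | Unchanged |

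The last two rows cannot be told apart in the table.

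**Step 2. How many subjects have inflamed gingiva at entry?** The inclusion criterion (Protocol 5.1) is "Mean full mouth MGI of at least 2.0", on a site scale from 0 to 4. Let s be the share of sites scoring 1 or more. With equal site weights the mean cannot exceed 4s, so 4s ≥ 2 and s ≥ 2/4 = 50%. Every eligible subject therefore has inflammation at half or more of the sites scored.

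**Step 3. Reproduce the plan's detection figure.** Protocol 12.3 and SAP 2.5 use 1 − (1 − p)^n. For p = 5%:
- n = 40: 1 − 0.95^40 = 87.1%, as stated.
- n = 20: 1 − 0.95^20 = 64.2%, as stated.

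**Step 4. Apply the same formula to the gingiva row.** Only subjects whose gingiva is coded normal at baseline can contribute. Call their share q. The documents do not give q, so it is an assumption and the whole range is shown. The 5% event rate is taken to be the same whatever the baseline coding. The chance of counting at least one event is 1 − 0.95^(nq).

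| q | n = 40: subjects who can count | Chance | n = 20: subjects who can count | Chance |
|---|---|---|---|---|
| 0 | 0 | 0% | 0 | 0% |
| 0.10 | 4 | 18.5% | 2 | 9.75% |
| 0.25 | 10 | 40.1% | 5 | 22.6% |
| 0.50 | 20 | 64.2% | 10 | 40.1% |
| 1 | 40 | 87.1% | 20 | 64.2% |

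At q = 0 the count is 0 of 50 + 50 + 25 = 125 enrolled subjects, whatever the truth. The plan's 87.1% is reached for this row only if every inflamed gingiva is coded normal. A rule that also counted worsening from an abnormal baseline would give 87.1% and 64.2% at any q, provided the worsening is recorded.

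**Step 5. What do the other routes capture?**
- Adverse events: Protocol 9.1.1 requires deterioration of a condition present at screening to be recorded as an adverse event. With onset after the first dose, it is treatment-emergent under SAP 8.4.
- MGI and GSI: change from baseline is compared between arms at Days 14 and 28 (SAP 9.3.2.1), as means in the Efficacy Population. The summary statistics include the minimum and maximum change, but no count of subjects who worsened. A subject who leaves before Day 14 has no scheduled post-baseline MGI and is replaced (SAP 4.2 and 9.1.1).
- Listings: findings are shown by subject, without a rate by arm.
- Days 3, 7 and 21: Protocol 7.4 calls for mucosal irritancy to be scored for edema and erythema, without naming the sites or scale. The SAP summarises only OMAS ulceration and erythema.

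**The case against.** The strongest reply is that 8.8.2 is one descriptive table among several routes. A reader might infer that gingival worsening can never be counted in this trial, and the documents do not support that. Deterioration of a baseline condition has a defined path into the main adverse event tables at any visit, and Protocol 3.2.1 says adverse events may include changes seen on oral examination. MGI, GSI and bleeding on probing are scored and compared by arm, and raw tooth-site values are listed.

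A reader might also infer that the gingiva has no scored measure at Days 3, 7 and 21. That is not established either, because the edema and erythema score required at those visits is not defined well enough to say whether it includes the gingiva.

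The zero count depends on a coding convention that the documents do not state and that may sit in the case report form or Manual of Procedures. Where the gingiva is coded normal at baseline, later abnormality is counted. The unchanged column is also labelled accurately as a change in binary status, and SAP 8.1 plans no between-arm test on this table, so no inference is biased.

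All of this stands and confines the point to the 8.8.2 summary. It does not remove it. The adverse event route depends on someone judging and reporting the deterioration as an event, the MGI and GSI analyses give average change rather than subjects who worsened, and listings give no rates. Oral examination findings are named in the primary objective separately from adverse events, so their summary should be able to show worsening, as the two tables beside it do.

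**Conclusion.** The point holds for the SAP 8.8.2 table. Worsening of a structure already abnormal at baseline has no category there and is shown as unchanged. This follows from the text and needs no assumption.

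Its size for the gingiva depends on how study gingivitis is coded at baseline. If it is coded abnormal in every subject, the treatment-emergent count in this table is zero by construction. If a share q is coded normal, the chance of counting at least one true 5% event in a 40-subject arm runs from 0% at q = 0 to 87.1% at q = 1. Coding as abnormal is likely, given that at least half of the sites are inflamed in every eligible subject, but it remains an assumption.

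Gingival worsening is not lost to the trial as a whole. This is an inexpensive improvement to a safety summary that serves the primary objective, not a failure of the safety evaluation.

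**What to change.** In SAP 8.8.2:
1. Extend the treatment-emergent definition to include a new or worse abnormality in a structure that was abnormal at baseline, classified before unblinding from the recorded descriptions.
2. Add a worsened column for each structure, as in 8.8.3 and 8.8.4.
3. State how study gingivitis is coded on the baseline oral exam. Without this the gingiva row cannot be interpreted.
4. For the gingiva, tabulate by arm in the Safety Population the number of subjects whose MGI or GSI rose from baseline at Days 14 and 28, with the number missing. This count should be read between arms, since some rises will be ordinary measurement variation.

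The cost is SAP wording, one extra table and a short masked review of descriptions. No new procedures or data are needed. The drawback is some subjectivity in the review, and its value depends on how much detail was recorded. Item 4 does not rely on the descriptions, but it cannot cover subjects who leave before Day 14. For them the adverse event records and listings remain the source.

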8.8.3 Oral Mucositis Assessment Scale Ulceration and Erythema Scores

The Oral Mucositis Assessment Scale (OMAS) score for ulceration and erythema will be listed for each oral structure by subject and visit. A table will summarize by the number and percent of subjects for each oral structure with ulceration and erythema scores that worsen, improve, or stay the same from baseline. The table will also summarize the number and percent of subjects with the OMAS scores missing due to early withdrawal or otherwise.

8.8.4 Tooth Status

The tooth status will be listed for each tooth by subject and visit. A table will summarize by the number and percent of subjects and by the number and percent of teeth for each tooth attribute at each study visit that worsen, improve, stay the same from baseline, or have missing values due to early study withdrawal or otherwise. Tooth status attributes recorded include: missing, sound, decayed, filled, fractured, crown, and dental implant.

9. EFFICACY EVALUATION

9.1 Overview of Efficacy Analysis Issues

9.1.1 Handling of Dropouts and Missing Data

Subjects that dropout or are withdrawn prior to Day 14 will be replaced in the Efficacy Population. The mixed models analyses (described in the sections below) will automatically adjust for any missing values provided the missing values are missing at random; and thus, no additional imputation is necessary for missing values that are missing at random.

Missing observations are “not missing at random” if their missing-ness is possibly correlated with disease progression or efficacy. Missing efficacy observations due to missed visits or early study withdrawal will be deemed “not missing at random” if there were any treatment-emergent AE (TEAE) prior to or concurrent with a subject’s missed visit and the relationship between the TEAE and study drug was rated as “Possible”, “Probable”, or “Definite”.

If more than 5% of a given efficacy endpoint is missing, or any missing observations are deemed “missing not at random” then a sensitivity analysis will be performed by repeating the given efficacy analysis with all missing values imputed using “last observation carried forward”. The sensitivity analysis will also be triggered if for any other reason the principle investigator suspects that missing values may bias the analysis. The reasons any sensitivity analyses are triggered will be footnoted in the sensitivity analysis tables.

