4.1 Safety Population

The Safety Population will consist of all subjects who are randomized into a study arm and complete their Baseline Visit. For the safety evaluations, subjects will be analyzed according to the treatment actually received. Any subjects that in error were administered both the BLXA4-ME and the placebo rinse at different times during the study will be analyzed in the BLXA4-ME treatment arm. Subjects that in error were administered both the non-rinse control treatment and either the BLXA4-ME or placebo rinse will be analyzed according to the rinse administered.

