4.2 Efficacy Population

The Efficacy Population will consist of all subjects of the Safety Population who have a baseline and at least 1 post-baseline assessment of 1 or more of the secondary efficacy outcome measures. Subjects that dropout or withdraw prior to Day 14 will be replaced in the efficacy population. For the efficacy evaluations, subjects will be analyzed according to the treatment actually received. Any subjects that began the study administering the treatment for one of the study arms and then later in error switched treatments to another study arm will not be included in the efficacy population.

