8. SAFETY EVALUATION

8.1 Overview of Safety Analysis Methods

All safety analyses will be carried out using the Safety Population.

- Adverse events (AEs)
- Unanticipated problems
- Vital signs
- Laboratory determinations (hematology, serum chemistry, and urinalysis)
- Physical examinations
- Dental examinations

With the exception of the progression of periodontitis based on the dental examinations, no statistical comparisons between the treatment groups are planned for the safety variables.

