8.2 Progression of Periodontitis

Progression of periodontitis will be defined as an increase of 2 mm or more in pocket depth (PD) or clinical attachment level (CAL) from the Day 0 baseline measurement. The frequency (percent) of subjects with progression of periodontitis will be summarized by study arm, visit, and overall. Generalized linear mixed models regression based on a binomial distribution and logit link will compare the odds ratios of the overall incidence of the progression of periodontitis among the study arms at the Day 14 and Day 28 time points. The results of the generalized linear mixed model will be presented in a table and include p-values and odds ratios (with 95% CI) for the treatment arm comparisons at the two study visits. The p-values will not be adjusted for multiplicity.

The generalized linear mixed models analyses will automatically adjust for any missing values provided the missing values are missing at random; and thus, no additional imputation is necessary for missing values that are missing at random.

Missing observations are “not missing at random” if their missing-ness is possibly correlated with disease progression or efficacy. Missing PD or CAL observations due to missed visits or early study withdrawal will be deemed “not missing at random” if there were any treatment-emergent AE (TEAE) prior to or concurrent with a subject’s missed visit and the relationship between the TEAE and study drug was rated as “Possible”, “Probable”, or “Definite”.

If more than 5% of the PD or CAL measures are missing, or any missing PD or CAL measures are deemed “not missing are random”, then a sensitivity analysis will be performed by repeating the above generalized linear mixed model with all missing values imputed as having progression of periodontitis. The sensitivity analysis will also be triggered if for any other reason the principal investigator suspects that missing values may bias the analysis. The reasons a sensitivity analysis is triggered will be footnoted in the sensitivity analysis table.

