9.2.2 Secondary Efficacy Endpoints

At baseline, study Day 14, and study Day 28, the following secondary efficacy variables: modified gingival index (MGI), bleeding on probing (BOP), IL-1 β , plaque index (PI), plaque severity index (PSI) and gingivitis severity index (GSI) will be recorded. PI, MGI, and BOP will be scored for each of the 6 tooth-sites for each tooth. IL-1 β will be measured in the GCF collected from one tooth (assigned by algorithm) in each quadrant. All efficacy analyses will be performed on the Efficacy Population.

The time point of greatest interest would be Day 28, but analysis will also be performed for Day 14.

The exploratory analysis pocket depth (PD) and clinical attachment level (CAL) will be descriptive.

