Since this is a safety phase 1 / 2 with safety measures as the primary endpoints, the secondary efficacy endpoints will not be adjusted for multiplicity. However, the contrast between the treatment and placebo rinse arms with respect to the MGI change from baseline at Day 28 will be considered the secondary endpoint of chief importance. The same statistical contrast but with BOP change from baseline as the dependent variable will be considered the statistical contrast next in order of importance.

Tables will summarize the p-values, contrasts, and least squares means (with standard errors) of the change from baseline and their differences among the treatment groups and visits for each of the mixed models analyses described above.

Summary statistics of the secondary endpoints and their change from baseline, including n, means, minimums, maximums, standard deviations, and standard errors, will be summarized in a table by study arm and study visit. Raw values of all the secondary efficacy endpoints, both on the tooth-site level and the subject level will be listed.

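### The two missing-data checks do not test what they need to: LOCF cannot show whether the Day 28 MGI contrast relies on dropouts keeping their benefit, and counting all missing values as progression does not bound the between-arm odds ratio

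*SAP*

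**What the plan says.** **Efficacy.** SAP 9.1.1 relies on mixed models that are valid if data are missing at random (MAR). A further analysis is triggered if more than 5% of an endpoint is missing, if any value is deemed not missing at random (a related adverse event before or at the missed visit), or if the principal investigator suspects bias. Then "a sensitivity analysis will be performed by repeating the given efficacy analysis with all missing values imputed using" LOCF. The other sensitivity analyses concern the dropped periodontitis exclusion (SAP 9.3.2.2) and GEE versus mixed models (SAP 9.3.3). Neither addresses data that are not missing at random.

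Efficacy is measured at baseline, Day 14 and Day 28. SAP 4.2 adds: "Subjects that dropout or withdraw prior to Day 14 will be replaced in the efficacy population". On timing, SAP 9.2.2 says: "The time point of greatest interest would be Day 28". SAP 9.3.2.1 ranks first "the contrast between the treatment and placebo rinse arms with respect to the MGI change from baseline at Day 28".

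**Progression.** SAP 8.2 uses a generalized linear mixed model that "will compare the odds ratios of the overall incidence of the progression of periodontitis among the study arms" at Days 14 and 28. Under the same triggers the check consists of "repeating the above generalized linear mixed model with all missing values imputed as having progression of periodontitis". SAP 8.1 makes this the one compared safety variable: "With the exception of the progression of periodontitis based on the dental examinations, no statistical comparisons between the treatment groups are planned". The population here is wider than for efficacy: "The Safety Population will consist of all subjects who are randomized into a study arm and complete their Baseline Visit".

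**The concern.** A missing-data sensitivity analysis should change the assumption in doubt and show whether the conclusion survives.

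For MGI, the doubt the SAP itself raises is that subjects leave for reasons linked to the drug or the disease. LOCF gives those subjects their last on-treatment value. If benefit is present at Day 14, LOCF and the MAR model will agree whether or not benefit is later lost, and the agreement could be read as robustness. SAP 9.3.2 intends these estimates for planning later trials.

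For progression, setting all missing values to the bad outcome looks conservative. It is conservative for a single arm's rate. A comparison of arms has no such guarantee, because the same rule also adds events to the comparator. Progression is part of the primary safety outcome (protocol 3.2.1 and 12.5.1), so a check that shrinks a real imbalance matters.

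**Working it through.** **Plan's own figure.** Inputs from SAP 2.5: SD 0.3, within-subject correlation 0.3, difference 0.2, alpha 0.05 (taken as two-sided). SD of change = 0.3 × √(2 × 0.7) = 0.355. Power is 71.2% for 40 versus 40 and 53.9% for 40 versus 20, against 70.9% and 53.8% stated. The inputs reproduce.

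**1. MGI at Day 28.** Assumptions: 50 per arm with a Day 14 value, a fraction f missing Day 28 in each arm, and the full 0.20 benefit present at Day 14 and in completers at Day 28.

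- LOCF contrast: (1−f) × 0.20 + f × 0.20 = 0.20 for any f.
- Contrast if active-arm dropouts return to the placebo mean: (1−f) × 0.20.
- MAR standard error: variance given baseline = 0.09 × (1 − 0.09) = 0.0819; Day 14–28 partial correlation r = (0.3 − 0.09)/0.91 = 0.231; SE² = 2 × 0.0819 × [(1−r²)/(50(1−f)) + r²/50].
- Tipping delta (the worsening of imputed active-arm values at which significance is lost): (0.20 − 1.96 SE)/f with the SE held fixed. The second figure in the last column solves 0.20 − f·delta = 1.96 √(SE² + f(1−f)delta²/50), which includes the variance that delta adds.

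| f (assumed) | LOCF | Benefit lost | MAR SE | Shift in SEs | Tipping delta |
|---|---|---|---|---|---|
| 5% | 0.20 | 0.19 | 0.0586 | 0.17 | 1.70 / 1.25 |
| 10% | 0.20 | 0.18 | 0.0602 | 0.33 | 0.82 / 0.69 |
| 20% | 0.20 | 0.16 | 0.0637 | 0.63 | 0.38 / 0.35 |

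A simulation (4,000 trials, ANCOVA, 20% missing, benefit lost in active-arm dropouts) gave −0.200 for LOCF, −0.199 for complete cases and −0.158 for the true Day 28 values.

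**2. Progression odds ratio.** The documents give no progression rate, so all counts are illustrative. Simple 2×2 odds ratios stand in for the mixed-model ones. There are 50 per arm.

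| Missing, active / placebo | Observed | Observed OR | All missing = progression |
|---|---|---|---|
| 10 / 10 | 6/40 vs 2/40 | 3.35 | 16/50 vs 12/50: 1.49 |
| 5 / 10 | 6/45 vs 2/40 | 2.92 | 11/50 vs 12/50: 0.89 |
| 10 / 5 | 6/40 vs 2/45 | 3.79 | 16/50 vs 7/50: 2.89 |

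In the first row the two extreme allocations are:

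- only active missing values progress: 16/50 vs 2/50, (16/34)/(2/48) = 11.3;
- only placebo missing values progress: 6/50 vs 12/50, (6/44)/(12/38) = 0.43.

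The planned check reports 1.49 from inside this range and marks neither end.

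With no true difference (5% in each arm), the imputed proportion is f + (1−f) × 0.05. Missingness of 10% active and 20% placebo gives 0.145 vs 0.24, OR 0.54. The reverse gives OR 1.86.

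**The case against.** **What stands.** Efficacy is secondary, unadjusted for multiplicity and openly underpowered. LOCF is a triggered addition to a mixed model that is still reported. The MGI shift depends on a target the SAP never states. At 5% or 10% missing, the worsening needed to lose significance is more than twice the assumed SD of 0.3, so the conclusion would be hard to overturn. For progression, the SAP does not claim to bound the odds ratio. Protocol 12.1 plans no formal safety testing, and protocol 12.5.1 reports incidence by arm, for which the rule is a valid upper bound. A withdrawal visit (protocol 7.7) may reduce missing measurements, and the SAP's reporting of non-missing n and withdrawals by arm lets a reader recover much of the missing count. All of this limits the size of the problem. It does not make either check informative about the comparison it accompanies.

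**What a reader might infer but should not.**

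- *That LOCF understates the standard error.* LOCF's SE (about 0.057) is smaller than the MAR model's, but that compares two different estimators. Simulated under the SAP's own SD and correlation, with equal effects at Days 14 and 28, LOCF's mean reported SE (0.057–0.058) matched its sampling SD (0.058–0.059), with 94–95% coverage at 5%, 10% and 20% missing.
- *That 20% is the most that can be missing at Day 28.* SAP 2.5 gives 20% attrition as a planning assumption. Missed visits add to it, and replacement of early dropouts reduces it in the Efficacy Population.

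**Conclusion.** The concern holds for both checks. LOCF cannot show whether the Day 28 MGI contrast depends on dropouts keeping their benefit. Where loss of benefit counts as part of the effect, the difference is 0.01, 0.02 or 0.04 MGI units (up to about 0.6 SE) at an assumed 5%, 10% or 20% missing. Where the target is the effect with rinsing continued, 0.20 is right and there is no bias. This assumes the full benefit is present at Day 14. In a side case, a subject without a Day 14 value for an endpoint would have baseline carried forward.

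The progression rule bounds each arm's rate but not the odds ratio. With equal missingness it pulls a real imbalance towards 1, and with unequal missingness it can move the ratio either way. Its size here is unknown, because rates and missing splits are assumed.

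The main observed-data analyses and the stated power are unaffected. The change is worth making before database lock, but the trial's main result does not depend on it.

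**What to change.** **SAP 9.1.1.** State whether loss of benefit after dropout counts as part of the effect. Replace LOCF with a delta-adjusted tipping-point analysis for Day 28 MGI, active versus placebo. Use multiple imputation under MAR, then add delta to imputed BLXA4-ME values in steps of 0.1 until the conclusion changes or imputed MGI reaches 4, the top of the scale. Report the estimate and confidence interval at each step. The grid must not stop early: in simulation at delta 0.4, estimate/SE was still 3.00 at 5% missing and 2.51 at 10%.

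Jump-to-reference imputation from the placebo arm may be added. Its SE should come from a bootstrap, or carry a note that Rubin's rules overstate its repeated-sampling variability (by about 20–25% at 20% missing in simulation).

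**SAP 8.2.** Keep the observed-data model. Label the existing all-missing result as an upper bound on each arm's rate. Add a two-way table of the Day 28 odds ratio, by number of missing BLXA4-ME subjects counted as progression and number counted in the comparator. Label both corners as extremes and print missing PD/CAL counts by arm.

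**Cost.** SAP wording and modest SAS programming, with no new data. Extreme cells will look strong even with no effect: 2/40 in each arm with 10 missing per arm gives corners of 7.6 and 0.13, hence the labels. If jump-to-reference is used with Rubin's rules, its SE is conservative.
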